9.1. Safety Measures

As this study is a non-interventional study, the primary interest of this study centres around the definition of the participant's CHR symptomatology. This will be tracked using the PSYCHS assessments which will include an assessment of symptom severity, but not assessment of causality or seriousness (or allocation to a specific diagnosis other than CHR status). Similarly, relevant medical history will be deemed as that reported during the baseline assessment. Further relevant medical history and adverse events will not be reported unless adverse events reported by the participant and/or other study team members are deemed to possibly having been caused by study activities (e.g., distress during interview, or because of interaction with study team).

The PI is responsible for ensuring that all study staff are aware of the following definitions and procedures:

9.2. Definitions

There will be no adverse events recorded in this study other than those outlined in the section above. Only the reports of those adverse events which are reported by the participant and/or study team member(s) as possibly having been caused by the study activities (e.g. distress during interview, or because of interaction with study team) will include separate individual assessment of seriousness and causality (all others: managed using the study assessments). If any of these self- or team-reported adverse events – causally or possibly causally related – meet standard seriousness criteria, they will be recorded and tracked as serious adverse events as per the Safety Management Plan.

9.2.1. Serious Adverse Event (SAE)

Hospital admissions which are related to an exacerbation in CHR symptomatology will not be reported as adverse events unless deemed to be causally related to the research activity.

9.3. AE and SAE Assessment

9.3.1. Causality

The causality of AEs (i.e., their relationship with study assessments) must be assessed by a suitably qualified Investigator at the study site. Assessing causality requires considering whether there was a reasonable possibility that the event may have been caused by study participation.

While in most cases, it is very difficult to categorically rule out a causal relationship, where terms such as “related,” “possibly related” and “not related” are used they will be interpreted as follows:

“related” - the reviewer is confident of the causal relationship (e.g. temporal association, existing safety knowledge of the product, clinical judgement);

“possibly related” - the reviewer is not confident of the causal relationship but tends to deem there is a positive causal relationship;

“not related” - the reviewer has no reason to believe there is a causal relationship at the time of the assessment (or tends to deem there is not a positive causal relationship).

Causality of an event may be re-evaluated by the reviewer at any time, e.g. when further evidence becomes available to confirm or refute an assessment of causality. The reviewer may be any person on the study team who has been delegated this responsibility by the Investigator.

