9.5. Expedited and Prompt Reporting of SAEs

Any serious adverse event (causally related, as defined above) occurring during the course of the study must be reported to the Sponsor (Orygen) within 24 hours of the Investigator or designee becoming aware of the SAE. As much information as possible, as is available at the time of recording, is to be provided. The Investigator should always provide an assessment of causality at the time of the initial report. A follow-up report should be completed when outstanding information becomes available, when there is a significant change in the event or when the event resolves. The Investigator will maintain an SAE Log including all SAEs. SAEs will be reported to the governing Human Research Ethics Committee (HREC) and/or governance institutions in accordance with HREC and institutional requirements and Orygen’s Safety Management Plan.

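### Section 9.3.1 applies two conflicting causality thresholds, so a serious event with a reasonable possibility of study causation can be coded 'not related' and miss SAE status and 24-hour reporting

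*Protocol*

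**What the plan says.** Section 9.3.1 opens with the test: "Assessing causality requires considering whether there was a reasonable possibility that the event may have been caused by study participation". It then defines three ratings. *Related* needs a reviewer confident of the causal relationship. *Possibly related* applies when "the reviewer is not confident of the causal relationship but tends to deem there is a positive causal relationship". *Not related* applies when the reviewer has no reason to believe in a causal relationship, and a parenthesis adds a second route: "or tends to deem there is not a positive causal relationship".

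On who rates, the section says causality "must be assessed by a suitably qualified Investigator at the study site". It closes by allowing the reviewer to re-evaluate at any time and by stating: "The reviewer may be any person on the study team who has been delegated this responsibility by the Investigator".

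Two later steps depend on the rating. Section 9.2 records and tracks as SAEs those self- or team-reported events that meet seriousness criteria and are "causally or possibly causally related". Section 9.5 sets the 24-hour report to the sponsor for "Any serious adverse event (causally related, as defined above"), so its wording names only the causally related and relies on a cross-reference for the rest.

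**The concern.** A causality scale should put into practice the test that the section sets. Here the two differ. A reasonable possibility is a low bar, and an assessor can accept it while still thinking another explanation more likely. *Possibly related* demands more, namely a lean towards causation, and the parenthesis in *not related* takes in every event where the lean goes the other way.

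This matters because the rating does more than describe an event. For a serious event it decides whether the event is tracked as an SAE and whether the sponsor hears of it within 24 hours. Section 9.3.1 itself acknowledges that a causal relationship can seldom be ruled out categorically, so uncertain cases are the expected ones, and these are the cases on which the two thresholds disagree. Section 10.1 provides no formal data safety and monitoring committee as a standing second look. Participants may be as young as 12 (section 7.4) and face about 9–10 hours of baseline assessment (section 6.4).

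**Working it through.** No arithmetic applies, and the protocol states no figure to reproduce. The check is to take each state of mind a reviewer can hold about a serious event and follow it through the text.

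| Reviewer's view | Meets the reasonable-possibility test? | Rating under 9.3.1 | SAE status under 9.2 | 24-hour report under 9.5 |
|---|---|---|---|---|
| Confident of causation | Yes | Related | Yes | Yes |
| Not confident, leans towards | Yes | Possibly related | Yes | Yes if 9.5 is read with 9.2; unclear on its wording alone |
| Sees a reasonable possibility, leans against | Yes | Not related, by the parenthesis | No | No |
| No reason to believe | No | Not related | No | No |

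**Third row.** The event passes the section's own test, but the only category whose definition fits is *not related*. The first limb of that category, no reason to believe, is compatible with the lead test. The parenthesis is what brings the conflict into the *not related* category, and the lean required by *possibly related* closes the other way out.

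**Entry to recording.** Section 9.2 puts the steps in this order: a participant or team member reports an event as possibly caused by study activities, and that event then receives its own assessment of seriousness and causality. Entry comes before the rating. Section 9.1 also speaks of events deemed possibly caused by study activities, but it names no rater and does not cite the 9.3.1 scale. The schedule of assessments lists adverse events at every visit from V2 to V16, and section 8.12 records events reported at contacts between visits. A later rating of *not related* therefore does not clearly remove an event from the adverse event record. What it can remove is SAE status and the expedited report.

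**Section 9.5.** None of the three ratings is called causally related. The cross-reference can point to the categories in 9.3.1, the nearest definitions above it, or to the SAE wording in 9.2, which covers both *related* and *possibly related*. The second reading is reasonable, but the text does not force it.

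**Who rates.** Section 9.3.1 requires a suitably qualified Investigator and then allows any delegated team member to be the reviewer who may re-rate. The delegate sentence states no qualification and does not separate the initial rating from a later downgrade.

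**The case against.** The strongest reply is that the consequences are narrow and other safeguards exist.

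- **Recording.** Section 9.2 admits events on a report of possible causation, before any rating, and interview distress is its own example of an event captured this way. A reader might infer that doubtful events drop out of recording altogether. The protocol does not support that.
- **Expedited reporting.** A reader might infer from 9.5 that only one of the three categories is expedited. That holds only if the cross-reference is ignored; read with 9.2, *possibly related* events are included. What remains is ambiguity, not a demonstrated exclusion.
- **Who assesses.** Section 9.5 expects the Investigator's causality assessment with the initial report, and section 12.2 requires staff to be qualified for their tasks. Re-rating can go in either direction and cannot undo a report already sent. The picture of an unqualified delegate erasing a reported SAE is speculative. The two sentences in 9.3.1 still need to be reconciled.
- **Follow-up.** Section 9.6 requires follow-up of study-related AEs and all SAEs, and section 7.10 has withdrawing participants asked about adverse events. A general loss of follow-up is not shown.
- **A numerical cut.** A reader might place the scale's cut at 50%. Neither the lead test nor the ratings are quantified, so that figure would be an assumption. The conflict does not need it: one test asks for a reasonable possibility, the other for a lean.
- **Other documents.** Section 10.1 provides regular review of AEs, SAEs and suicidality data involving medically trained personnel, and detail is left to a Safety Management Plan that is not shown. Practice may be better than the protocol's text, but neither alters the definitions printed in 9.3.1.

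These points limit the consequences. None of them removes the mismatch between the lead test and the categories.

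**Conclusion.** The concern holds as a conflict within section 9.3.1. A serious event with a reasonable possibility of study causation, but against which the reviewer leans, is coded *not related* and can miss SAE status under 9.2 and 24-hour reporting under 9.5. The conclusion rests on taking the definitions as printed and on those two sections depending on relatedness, as their wording says.

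The size cannot be given: the protocol offers no event rate and no basis for how often a reviewer would see a reasonable possibility yet lean against it. The point bears on participant safety. It affects no study outcome or analysis.

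**What to change.** In section 9.3.1, define *possibly related* as a reasonable possibility that study participation caused or contributed to the event, and *not related* as no reasonable possibility. Delete the parenthesis about leaning against a causal relationship.

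In section 9.5, replace the parenthetical condition with *related or possibly related*, so that it matches 9.2 without relying on a cross-reference.

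Reconcile the Investigator requirement with the delegate sentence by stating that any downgrade of a causality rating is made or countersigned by the suitably qualified Investigator.

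These are wording changes only. The downside is a few more events coded possibly related and reported, plus a countersignature when a rating is lowered.

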9.4. Recording of Adverse Events and Serious Adverse Events

Adverse events will be recorded and reported as per the per the Safety Management Plan (source documentation will include the study visit assessments, the Adverse Event Log and/or the Serious Adverse Event form).

9.5. Expedited and Prompt Reporting of SAEs

Any serious adverse event (causally related, as defined above) occurring during the course of the study must be reported to the Sponsor (Orygen) within 24 hours of the Investigator or designee becoming aware of the SAE. As much information as possible, as is available at the time of recording, is to be provided. The Investigator should always provide an assessment of causality at the time of the initial report. A follow-up report should be completed when outstanding information becomes available, when there is a significant change in the event or when the event resolves. The Investigator will maintain an SAE Log including all SAEs. SAEs will be reported to the governing Human Research Ethics Committee (HREC) and/or governance institutions in accordance with HREC and institutional requirements and Orygen’s Safety Management Plan.

9.6. Handling in Cases of Unresolved AEs and SAEs at Completion or Withdrawal

Where possible, all study related AEs and all SAEs must be followed up until resolution unless, in the Investigator’s opinion, the condition is unlikely to resolve.

9.7. Procedures in Case of Medical Emergency

The Principal Investigator is responsible for ensuring that procedures and expertise are available to manage medical emergencies during the study at the premises participants attend for study assessments.

9.8. Clinically Significant Results

The type of testing being conducted in this study is not designed to result in information about an individual participant or their family member's health. We will not provide participants with any individual results from analysis of the research samples. While we do not expect to identify clinically significant results in the samples, it is possible that findings of clinical significance to an individual's or their family member's health are incidentally identified.

Normal ranges for blood samples collected as part of this study are determined based on international consensus and population based studies. An allocated medically trained investigator will review the results and determine if they are clinically significant.

A radiologist will review all MRI scans and provide a report to an allocated medically trained investigator at each site, who will decide whether the scan may have clinical significance.

With regard to genetic analysis, a standard set of guidelines developed by the University of Queensland in line with The Human Genetics Society of Australasia (HGSA) position statement will be followed when determining and reporting incidental findings from genetic analyses <https://www.hgsa.org.au/documents/item/11030>.

Participants will be provided with the option of indicating if they would like to receive any incidental findings relating to their health or their family members' health. The information generated from their biospecimen and the genetic analyses may in some instances have recognised interventions that can benefit or reduce risk of harm to the participant or family members.

If an incidental finding is identified, the lab conducting the analysis or MRI scan will contact the research team so that the research team can link the participant's sample code with their personal details, enabling the team to contact the participant and their clinical team. The participant's clinical team or a suitably qualified study team member (medically trained) will contact the participant, and their parent/guardian if applicable, to let them know that an incidental finding of clinical significance was found and to offer them the option of learning about these results. If the participant and/or parent/guardian would like to know the details of these findings, the study team member will discuss the findings with them and advise on any clinical follow up that may be required. The study team member will arrange referrals for further clinical follow up as appropriate.

10. Study Oversight

10.1. Data Safety and Monitoring Committee

Due to the low-risk category of the study, as determined by the Sponsor, a formal Data Safety and Monitoring Committee will not be established. Safety and monitoring will be overseen by the Investigator team and Project Manager and managed in accordance with the Safety Management Plan as outlined in the Procedures Manual. Safety signals (AEs, SAEs, and suicidality data) will be regularly reviewed by study Project Manager/s and medically trained personnel. If required, and in consultation with the Sponsor, safety data will be reviewed by an independent committee to protect the safety and interests of participants included in the study.

11. Ethical Considerations

11.1. Review by an Ethics Committee

Prior to the commencement of the study, the protocol and any amendment(s), Participant Information and Consent Form, other information provided to participants (including advertising) and product information, will be submitted to the Institutional Human Research Ethics Committee (HREC). The approval letter should refer to the study by title, protocol number and version and dates of documentation reviewed and approved. A copy of the signed and dated letter of approval (on institutional letterhead) will be provided to the site and Orygen prior to study commencement.

During the course of the study, the Principal Investigator (or delegate)/Sponsor (or delegate) is required to submit to the HREC/RGO the following: amendments to the protocol and SAEs as per the committee's requirements, site-specific updates as agreed to by the Investigator and respective HREC/RGO, progress reports according to local regulations and guidelines, Final Study Report if applicable and any additional information as required (e.g., SAEs reported by other investigative sites, amendments safety information and significant administrative changes to the protocol).

Protocol amendments that may impact on participant safety or the validity of the study will be agreed upon by the PI and Sponsor and submitted to the reviewing HREC for approval prior to implementation. At conclusion of the study, the Investigator is required to inform the HREC in writing that the study has ended and no further activities regarding this protocol will be conducted at the site.

The Investigator will ensure that the study is performed in accordance with ethical principles that have their origin in the Declaration of Helsinki and are consistent with International Conference on Harmonisation (ICH) Good Clinical Practice (GCP). The National Health and Medical Research Council (NHMRC) National Statement on Human Research will also be adhered to in Australia (as will the equivalent guidelines in other countries be adhered to be those nations' investigator sites).

11.2. Ethical Conduct of the Study

This study will be carried out in accordance with the Principles of ICH-GCP (as adopted in Australian or the applicable local regulatory authorities) which build upon the ethical principles contained in the Declaration of Helsinki and the Australian NHMRC National Statement on Ethical Conduct in Human Research, and the NHMRC Australian Code for the Conduct of Research or relevant local equivalents.

11.3. Consultations with the Youth Research Council

At the sponsor level, regular meetings with the Orygen Youth Research Council will take place throughout the study as required. This will ensure ongoing engagement of youth in the study process. Feedback from the Youth Research Council will be recorded and considered for future amendments.

11.4. Investigator Responsibilities

The protocol and the informed consent form must be reviewed and approved by a properly constituted HREC before study start. A signed and dated letter that the protocol and informed consent have been approved by the HREC must be provided to Orygen before study initiation. Prior to study start, the investigator is required to sign the protocol signature page confirming his/her agreement to conduct the study in accordance with these documents and all of the instructions and procedures found in this protocol and to give access to all relevant data and records to Orygen monitors and auditors, HREC and regulatory authorities as required. If an inspection of the clinical site is requested by a regulator, the investigator must inform Orygen immediately that this request has been received.

Prior to participation in the research study, each participant (or participant and parent/legal guardian for participants under 18 years of age) will undergo a complete consenting interview with the delegated study team members and provide consent on the relevant HREC approved form. The contents and process of obtaining informed consent will be in accordance with all applicable regulatory requirements including those required for the consenting of participants considered under legal adult age

according to local laws. Investigators in countries other than Australia will adapt consent processes accordingly to meet local requirements (including ages of majority).

All eligible participants will have the study explained by the PI or the delegated Research Assistant or other study member. They will receive a full explanation, in lay terms of the aims of the study, the discomfort, risks and benefits in taking part as well as insurance and other procedures for compensation in case of injury. It will be explained that the study is for research purposes and may not provide benefit to the individual. It will be pointed out that they can withdraw from the study at any time without prejudice. Each participant will acknowledge receipt of this information by giving informed consent for participation in the study. Informed consent may also be provided electronically. The participant will be given a copy of the signed or electronically acknowledged Participant Informed Consent Form (PICF) to retain. All study documents will be fully approved by the HREC prior to being used for consenting purposes.

11.5. Participant Data Protection

The PICF will explain that study data will be safely stored in computer databases as well as in paper form. The maintenance of confidentiality will be in accordance with national data and privacy legislation. Participants in this database are identified by a unique participant identification number and their initials. The PICF will also explain that for data verification purposes, authorized representatives of Orygen, regulatory authorities, HREC/IRBs or sites may require direct access to parts of the hospital or practice records relevant to the study, including medical history.

12. Study Management

12.1. Monitoring and Auditing

Study monitoring will be performed in accordance with applicable regulations, ICH-GCP, and Orygen Standard Operating Procedures (SOPs). The level of monitoring required for the study will be based on a risk assessment of the study by Orygen.

During the course of the study, the Orygen monitor will regularly contact and may conduct remote visits to monitor study progress, confirm protocol, regulatory and ethical adherence, confirm data accuracy and provide information and support. The PI agrees to allow the monitor direct access to all relevant documents and to allocate their time and the time of their staff to the monitor to discuss findings and any relevant issues. Site staff will be provided with monitor and back up contact details in the event they have queries or require assistance.

An audit is a systematic and independent examination of study-related activities and documents to determine whether the approved study-related activities were conducted, and the data were recorded, analysed and accurately reported according to the protocol, Orygen SOPs and any applicable institutional requirement(s). Authorised representatives of Orygen, a regulatory authority, or the HREC may visit the site to perform audits or inspections. The Investigator should contact Orygen or designee immediately if they are contacted by a regulator about an inspection at their site. If an audit or inspection occurs, the PI and institution agree to allow the auditor/inspector direct access to all relevant documents and allocate their time and the time of their staff to the auditor/inspector to discuss findings and any relevant issues.

The Investigator will ensure that direct access to source data/documents for the purposes of monitoring, audits, HREC review and regulatory inspections is available throughout the study and during the record retention period. In addition, the Investigator will ensure that each study participant has consented, in writing, to their medical records for trial-related monitoring audits, HREC review and regulatory inspections.

